8.2 Subgroups EC and ENC within the Eeva plus morphology grading group

The EEVA Time Lapse system assists the embryologist in improving embryo assessment accuracy. Whether the embryologist follows the recommendation made by the system is the decision of the embryologist. Therefore two subgroups will be considered:

(a) Subjects form Eeva scores plus morphology grading group for whom the embryologist has followed the recommendation of the Eeva system (group noted EC or Eeva conform). As the principle selection algorithm for the test arm of the study the selection of embryos for transfer is based on the recommendations made by the EEVA system.

(b) Subjects form Eeva scores plus morphology grading group for whom the embryologist has NOT followed the recommendation of the Eeva system (group noted ENC or Eeva Not conform). Every effort at the site will be made to keep this case to a minimum of cases as investigators are encouraged to use their technical expertise and follow the EEVA system recommendations. However, on investigators' discretion and patients' best interests it may be decided to exceptionally disregard the system recommendation when such recommendation contradicts the morphological pre-assessment of the embryos.

PPD will share the "Embryo Days 2, 3, 5, 6 Laboratory Data Morphological/EEVA Grading" data with Merck after the database lock.

8.3 Added selection

The KID sample (Known Implantation Data) is the subset of ITT sample such that the IR=0% or 100% (for single,double or triple) mbryo transfer, ITT=KID; for other implantations, women such that $0 < IR < 1 < 2 < 3$ will be disregarded).

9 General Specifications for Statistical Analyses

10 Study Subjects

10.1 Disposition of Subjects and Discontinuations

This table will provide the distribution of the randomized patients for each group into completers and non completers. For completers, the table will provide the distribution of the type of completion (variable cycleCST, cfr section 19), and for non completers, the distribution of the reason of non completion (variable cycleNST, cfr section 19).

10.2 Protocol Deviations

Protocol deviations will be determined before database lock.

11 Demographics and Other Baseline Characteristics

11.1 Demographics, Medical History, Other Baseline Characteristics

Table will describe each group EMG and MG on all the above described existing variables at baseline. Depending on the type of variable, two-way Crosstab or Mean tables across (EMG/MG) Groups will be provided (cfr table contents and individual description of these tables in section 19).

11.2 Descriptive tables for post-baseline variables

For all the variables after baseline, each variable (described in table 19) will be documented for each subgroup (EMG/MG) according a frequency two-way cross tabulation or a mean table, depending on the type of variable (nominal, continuous).

12 Previous or Concomitant Medications/Procedures

Does not apply

13 Treatment Compliance and Exposure

Does not apply

14 Endpoint Evaluation

14.1 Primary analysis

Implantation rate will be analyzed with two definitions

First definition: The IR (at embryo level) corresponding to a group of patients is calculated as the ratio of the total fetal sacs (nFS) identified by ultrasonography at weeks 5 to 8 divided by the number of embryos transferred (nET), thus $IR = nFS/nET$.

Alternative Definition of Implantation Rate: The previous (and usual) calculation of IR as mentioned in the protocol ($IR = nFS/nET$) has problems, in particular the implanted embryos are not independent. The international definition used by WHO in particular (see for instance <http://www.advancedfertility.com/ivf.htm>) is: The alternative definition IR^* at women level is $IR_w = nFS_w/nET_w$ and $IR^* = (1/n) \cdot \sum_{w=1,n} IR_w$.

Note: The two definitions IR and IR^* coincide in some cases, in particular for elective Single Embryo transfer eSET (where only one embryo is transferred) or when KID sample is used, but in the general case (ITT sample for instance, IR and IR^* will be different).

The point estimate and 95% CI of IR and IR^* will be calculated in both groups EMG and MG for the ITT selection. No inferential comparison will be conducted between these two groups (as this study is purely descriptive).

The following sections are considered as secondary analyses.

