4.1 Primary

The primary objective of the trial is to compare the rate of implantation for Day 3/5 embryo transfers using Eeva scores plus morphology grading versus Day 3/5 embryo transfers using morphology grading only. Implantation rates are calculated by dividing the number of gestational sacs with fetal heart beat identified by ultrasonography at weeks 5 to 8 by the number of embryos transferred on Days 3 or 5.

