6.1 Endpoints

Primary Endpoint: Implantation rate from embryo transfers performed on day 3 or day 5.

Secondary Endpoints: Utilization rate, Clinical pregnancy rate, Ongoing pregnancy rate, Multiple pregnancy rate, Spontaneous miscarriage rate.

Endpoints are defined as follows :

- Implantation rate (number of sacs with fetal heart beat/ total number of embryos transferred)
- Utilization rate (transferred + frozen/ fertilized eggs) X100.
- Clinical pregnancy rate (at approximately 5-8 weeks gestational age)
- Multiple pregnancy rate defined as a clinical pregnancy with ≥ 2 fetal sacs.
- Spontaneous miscarriage rate as a desired follow-up endpoint.

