6.3.7 Gestational Age Week 5-8

The first ultrasound to verify clinical pregnancy will be recorded on the **Transfer and Treatment Outcome** eCRF including:

- Date of ultrasound
- Result of initial pregnancy ultrasound
 - Number of intrauterine gestational sacs
 - Number of fetal heartbeats

If the result of the ultrasound is negative, that is, if no fetal heartbeat is detected, then the subject will have completed the trial and be exited at that time (complete **Trial Exit** electronic case report form).

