7.4 Endpoints

7.4.1 Primary Endpoint(s)

The primary endpoint is the Implantation Rate from embryo transfers performed on day 3 or 5. The crude estimate of the implantation for each embryo assessment method (Eeva scores plus morphology grading, morphology grading only) will be calculated as the ratio of the total fetal sacs identified by ultrasonography at weeks 5 to 8 and the number of embryos transferred.

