7.6.2 Analysis of Primary Endpoint(s)

The crude estimate of the implantation for each embryo assessment method will be calculated as the ratio of the total fetal sacs identified by ultrasonography at weeks 5 to 8 and number of embryos transferred. The approximate 95 % confidence interval of implantation for each embryo assessment method will be calculated. The difference between the methods will be analyzed in an exploratory way using a Poisson regression model. Details regarding the model and analysis approach will be specified in the SAP.

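### The protocol defines the primary implantation rate with two different numerators, and the SAP estimates only the all-sac version, not the heartbeat version in the primary objective

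*SAP*

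**What the plan says.** The protocol gives the numerator in four places, and they split two against two.

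- Protocol 4.1, under the primary objective, obtains the rate by "dividing the number of gestational sacs with fetal heart beat identified by ultrasonography at weeks 5 to 8 by the number of embryos transferred".
- Protocol 6.1 agrees: "Implantation rate (number of sacs with fetal heart beat/ total number of embryos transferred").
- Protocol 7.4.1 has the rate "calculated as the ratio of the total fetal sacs identified by ultrasonography at weeks 5 to 8 and the number of embryos transferred", with no heartbeat condition.
- Protocol 7.6.2 repeats this for the analysis: "the ratio of the total fetal sacs identified by ultrasonography at weeks 5 to 8 and number of embryos transferred".

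SAP 14.1 takes the second version, the "ratio of the total fetal sacs (nFS) identified by ultrasonography at weeks 5 to 8 divided by the number of embryos transferred (nET"). It refers to this as the "calculation of IR as mentioned in the protocol". It then adds a second definition, IR*, which averages each woman's own rate, but that rate also has nFS on top. The SAP's abbreviation list expands nFS only as the number of foetal sacs. Under its heading on changes to the planned analyses, the SAP records none.

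**The concern.** A sac can be seen without a heartbeat, so the two numerators agree only if every sac has one. The trial is exploratory, and SAP 14.1 plans no inferential comparison for the primary analysis. Its whole primary result is therefore a rate and a confidence interval per arm. If that rate is not the one in the objective, a reader could take the reported figure for something it is not. Protocol 5.2 also wants realistic intervals from this trial to inform a later randomized trial, and those would rest on an endpoint with two meanings.

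The numerator also decides who is analysed. SAP 8.3 defines the KID sample as the "subset of ITT sample such that the IR=0% or 100" per cent. The EC/ENC, regression and subgroup results for implantation rate inherit the same count.

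**Working it through.** **1. Could fetal sacs be shorthand for sacs with a heartbeat?** The text does not support this.
- Protocol 6.3.9 and SAP 19.2.6 list fetal sacs and heartbeats as separate items.
- Within Protocol 6.1, implantation uses sacs with a heartbeat, while multiple pregnancy uses fetal sacs alone.
- Protocol 6.3.7 treats a scan with no heartbeat as negative and exits the woman. Under SAP 14.1, a sac seen at that scan still counts as an implantation.

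**2. Is a heartbeat-based rate planned anywhere?** No.
- SAP 14.1: IR and IR* differ only in averaging (per embryo or per woman); both use nFS.
- SAP 14.2 and 14.3 repeat IR and IR* for EC/ENC and KID.
- SAP 14.6 models and subgroups IR without naming another numerator.
- SAP 19.2.6 tabulates heartbeats by arm. This is not a rate per embryo transferred and has no interval.
- SAP 17 lists Nsac and Nhbt but no variable called nFS, so the derivation of the numerator is not stated.

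**3. Planned precision (Protocol 7.2).** The table follows from half-width = 1.96 × √(p(1−p)/n), with n in subjects. At p = 35%:
- n = 1000: 1.96 × √(0.35 × 0.65/1000) = 2.96 points (stated 3.0)
- n = 500: 1.96 × √(0.35 × 0.65/500) = 4.18 points (stated 4.2)

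All ten values in the table reproduce to one decimal.

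**4. Size of the gap.** Let s be the share of sacs without a heartbeat. The documents do not give s, so the values below are assumptions. Heartbeat rate = sac rate × (1 − s). From a sac rate of 35%:

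| s | Heartbeat rate | Gap (points) |
|---|---|---|
| 5% | 33.25% | 1.75 |
| 10% | 31.5% | 3.5 |
| 15% | 29.75% | 5.25 |
| 20% | 28.0% | 7.0 |

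Over the table's range of 25% to 45%, the gap runs from 25 × 0.05 = 1.25 to 45 × 0.20 = 9.0 points.

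**5. Share at which the gap equals the half-width** (half-width ÷ rate):

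| Sac rate | n = 1000 | n = 500 |
|---|---|---|
| 25% | 2.684/25 = 10.7% | 3.795/25 = 15.2% |
| 35% | 2.956/35 = 8.4% | 4.181/35 = 11.9% |
| 45% | 3.083/45 = 6.9% | 4.361/45 = 9.7% |

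Below these shares the gap is smaller than the half-width. The comparison is rough, because the half-widths count subjects while IR counts embryos.

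**6. KID membership, two embryos transferred:**
- One sac, no heartbeat: 1/2 = 50% on sacs (excluded); 0/2 = 0% on heartbeats (included).
- Two sacs, one with a heartbeat: 2/2 = 100% on sacs (included); 1/2 = 50% on heartbeats (excluded).

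Membership can therefore change in either direction.

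**7. Comparison between arms.** If s is the same in both arms, the ratio of rates is unchanged and the difference is multiplied by (1 − s).

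**8. Can the heartbeat numerator be built from the collected counts?** Nhbt counts heartbeats, not sacs, so one sac with two heartbeats would be counted twice. Capping Nhbt at Nsac per woman handles this. Enumerating 0 to 3 sacs with 0 to 2 heartbeats each, the cap equals the number of sacs with a heartbeat whenever Nsac or Nhbt is 0 or 1. It can overcount only when both are at least 2: Nsac = 2 and Nhbt = 2 can mean one or two sacs with a heartbeat.

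**The case against.** The strongest reply is that little depends on the choice. The trial is exploratory; no primary test, sample size or decision rule uses the numerator; and both counts are collected, so either rate could be computed later. That is correct, and it limits the harm. It does not remove it: the descriptive rate is the primary result, and a rate chosen after the data are seen is no longer prespecified.

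Second, the SAP follows Protocol 7.6.2 closely, so its statement that nothing changed is accurate for that section. This stands. The contradiction begins inside the protocol, and the SAP carries one side of it forward without resolving it.

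Third, some of the evidence on wording is weaker than it looks. Protocol 6.3.7 ("Number of intrauterine gestational sacs") and SAP 17 set gestational sacs, not fetal sacs, beside heartbeats. They show that both counts exist but not what a fetal sac means. Protocol 6.1 and 6.3.9 and SAP 19.2.6 carry that point, and they are enough.

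Fourth, SAP 19.2.6 tabulates heartbeats and embryos transferred by arm, so a reader could work out a crude rate. That is true, but it is neither planned as a result nor given an interval.

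**Conclusion.** The concern holds and must be fixed. The protocol gives the primary endpoint two numerators that agree only if every sac has a heartbeat. The SAP adopts the one that is not in the primary objective, and no planned analysis yields the objective's rate with a confidence interval. The direction is certain: the SAP rate equals or exceeds the rate in Protocol 4.1 and 6.1. The size is unknown, and the figures above are illustrations resting on an assumed share of sacs without a heartbeat. Bias between arms would need that share to differ by arm, for which the documents give no evidence. The sample size is unaffected.

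**What to change.** Before database lock, state one numerator in Protocol 4.1, 6.1, 7.4.1 and 7.6.2 and in SAP 14.1, for both IR and IR*. The heartbeat version is the natural choice, because it matches the primary objective and the endpoint definition. Define it as the number of sacs with at least one heartbeat and put the derivation in SAP 17, for example Nhbt capped at Nsac per woman. Check women with both counts at 2 or more against the scan report. The derivation should also say that only heartbeats in intrauterine sacs count, because Protocol 6.3.7 restricts sacs but not heartbeats to intrauterine and SAP 17 records ectopic pregnancy as an outcome. Use the same numerator for KID, EC/ENC, the regression and the subgroups. Report the all-sac rate with its 95% CI as a labelled sensitivity result.

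The cost is wording, one derived variable and a limited source check; no new data are needed. The protocol edits may count as a major amendment under Protocol 9.9, with the submissions that entails. The headline rate may be somewhat lower. Without the source check, the cap is only an upper bound in women with two or more sacs and two or more heartbeats.

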7.2 Interim Analysis

Interim analysis was planned when half of the patients completed the study in the protocol. But based on medical affairs advice it was decided not to conduct the interim analysis.

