14.6 Exploratory Variables

Multiple Linear regression analysis of IR (based on subject level) as dependent variable and treatment as independent parameter effected by the following confounding factors

Factors	Description
Stimulation protocol	Categorical variable, 3 states: Agonist Luteal phase; Antagonist; and Agonist Mirco-dose Flare and Other
Drugs used	Categorical variable, 3 states: recombinant Gn, urinary Gn, and mix-use of recombinant and urinary Gns
Day of transfer	Categorical variable, 2 states: D3 Vs D5/6
Age of patients	Continuous variable , years
Culture medium	Categorical variable, 5 states: Quinn's Advanced Fertilization, Global Medium, Vitro life G-IVF, Irvine Single Step Medium, and Other

A better estimate of implantation rate will be obtained based on subject level adjusted for confounding factors by a Multiple Linear regression.

Given the exploratory nature of the design, the model will be investigated stepwise and repeated backward. The final model will exclude backward P-values > 0.10.

The Center effect will also to be considered in the model.

The results of regression analysis will be reported with the following items

- Regression Coefficient with 95% CI
- Standard Error
- P-value
- Coefficient of Determination (R^2)

Subgroup analyses

Further subgroup analysis based on selected baseline parameter could be conducted as follows.

- 1) IR of the two treatment groups at each site (descriptive summary statistics with 95% CI,

and RR with 95% CI and P value). The Risk Ratio, 95% CI and P-value will be calculated, provided the number of subjects in a site will be at least 30, otherwise only descriptive statistics will be provided for that particular site.

- 2) IR, CPR, OPR and SMR of the two treatment groups for subgroups of patients with ET on D3 and D5/6 (descriptive summary statistics, RR with 95% CI and P value);
- 3) IR, CPR, OPR and SMR of the two treatment groups for subgroups of patients with age ≤35 and >35(descriptive summary statistics, RR with 95% CI and P value).
- 4) IR of the two treatment groups for subgroups of patients using 5 types of culture media (descriptive summary statistics, RR with 95% CI and P value).
- 5) IR of subgroups of patients using 5 types of culture media (regardless the method of embryo assessment, descriptive summary statistics and 95% CI)

15 Safety Evaluation

In conformity with protocol, device deficiency will be individually listed.

16 References

No reference at this stage

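### The SAP leaves the protocol's exploratory overall comparison of implantation rates out of the primary analysis and declares no change

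*SAP*

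**What the plan says.** Protocol 4.1 sets a comparative objective: "The primary objective of the trial is to compare the rate of implantation for Day 3/5 embryo transfers" between the two selection methods. Protocol 7.6.2 asks for a crude rate and an approximate 95% CI per method, and then adds: "The difference between the methods will be analyzed in an exploratory way using a Poisson regression model". What it hands over is limited: "Details regarding the model and analysis approach will be specified in the SAP".

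SAP 5.1 restates the primary objective as point and interval estimates in each group. SAP 14.1 plans those estimates under two definitions. IR is total fetal sacs over total embryos transferred (nFS/nET). IR* is the mean over women of each woman's own ratio. The section then says: "No inferential comparison will be conducted between these two groups (as this study is purely descriptive", and it classes everything after it as secondary.

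The entry on changes to the planned analyses, which follows SAP 7.3, reports none. SAP 7.2 does record another departure, the cancelled interim look: "But based on medical affairs advice it was decided not to conduct the interim analysis".

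SAP 14.6 plans a "Multiple Linear regression analysis of IR (based on subject level) as dependent variable and treatment as independent parameter", with stimulation protocol, drugs, day of transfer, age and culture medium as confounders and centre also to be considered. Its selection rule reads: "The final model will exclude backward P-values > 0.10". The same section lists optional between-arm risk ratios with P-values by site, transfer day, age and culture medium.

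**The concern.** The primary analysis as written does not answer the primary objective, even in the exploratory sense that the protocol intends. The protocol had already labelled the Poisson comparison exploratory, so that label does not explain its removal. Delegating the details of a model is not the same as delegating whether the difference is analysed at all.

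The trial is meant to generate hypotheses for a later randomised trial, and protocol 5.5 justifies the control arm by that comparison. The overall contrast with its interval is a quantity on which such a trial would be planned. Under the SAP a reader must construct it from two separate intervals or take it from an adjusted secondary model. Because the SAP declares no changes, the reader is not told that the plan has moved.

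The stated reason, that the study is descriptive, also sits badly with SAP 14.6. That section allows between-arm ratios and P-values in subgroups, while the primary analysis bars the overall one.

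**Working it through.** **Text, side by side**

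- Objective: comparative in protocol 4.1; estimation within each group in SAP 5.1.
- Overall contrast: exploratory Poisson regression in protocol 7.6.2; barred in SAP 14.1, with no Poisson model elsewhere in the SAP.
- SAP 14.2 to 14.5: estimates and intervals per group only.
- SAP 14.6: a treatment coefficient with 95% CI, SE and P-value from a linear model on woman-level IR. This is the only overall EMG-MG contrast left. Its covariates depend on the selection rule. One candidate, day of transfer, is settled after enrolment on day 1 (protocol 8.2).
- Record of change: the interim analysis is disclosed in SAP 7.2; the loss of the Poisson comparison is not recorded as a departure.

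**Precision of the contrast that is not reported**

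Inputs from protocol 7.2: 1000 EMG and 500 MG women, and rates of 25% to 45%. The protocol's own table gives per-arm half-widths, and 1.96 × √(p(1−p)/n) reproduces all ten entries. For one binary outcome per woman, the half-width of the difference is 1.96 × √(p(1−p)(1/1000 + 1/500)).

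| Rate | n=500: stated, recomputed | n=1000: stated, recomputed | Half-width of difference |
|---|---|---|---|
| 25% | 3.8, 3.80 | 2.7, 2.68 | 4.65 |
| 30% | 4.0, 4.02 | 2.8, 2.84 | 4.92 |
| 35% | 4.2, 4.18 | 3.0, 2.96 | 5.12 |
| 40% | 4.3, 4.29 | 3.0, 3.04 | 5.26 |
| 45% | 4.4, 4.36 | 3.1, 3.08 | 5.34 |

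As a ratio, the 95% limits lie a factor exp(1.96 × √(((1−p)/p)(1/1000 + 1/500))) either side: 1.20 at 25%, 1.16 at 35%, 1.13 at 45%.

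**Allowing for several embryos per woman**

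The documents give neither the distribution of embryos transferred nor the within-woman correlation r. SAP 8.3 mentions triple transfers, so I let m, the number per woman, run from one to three and r from 0 to 1. The implantation probability is taken not to depend on m.

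- nFS/nET scale: variance factor E[m(1+(m−1)r)] / (E[m])².
  - Smallest (all women with three, r = 0): 3/9 = 1/3, so 5.12 × √(1/3) = 2.96 points.
  - Largest (a quarter with three, the rest with one, r = 1): E[m²] = 0.75 + 0.25 × 9 = 3 and E[m] = 1.5, so 3/2.25 = 4/3 and 5.12 × √(4/3) = 5.91 points.
- IR* scale: variance factor E[(1+(m−1)r)/m], from 1/3 to 1, so 2.96 to 5.12 points.
- Rate ratio on nFS/nET at 35%: exp(2.96/35) = 1.09 to exp(5.91/35) = 1.18.

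**Can a reader recover the difference?** Approximately. At 35%, √(4.18² + 2.96²) = 5.12, the same half-width. A reader who looks only for overlap of the two intervals would instead require a gap of 4.18 + 2.96 = 7.14 points.

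**The case against.** The strongest reply is that nothing essential is lost. SAP 14.6 reports an overall treatment coefficient with its interval, and the SAP presents the model as an improvement: "A better estimate of implantation rate will be obtained based on subject level adjusted for confounding factors by a Multiple Linear regression". Protocol 7.6.2 lets the SAP settle the model and approach, so a move from Poisson to linear regression is arguably within its remit. Woman-level IR is the component of IR*, which SAP 14.1 adopts because embryos in one woman are not independent. The trial has no stated power or effect size, and protocol 5.2 and 7.2 speak of confidence intervals and per-arm precision. The arms are independent, so the unadjusted difference can be derived.

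Much of this stands. A reader might infer that the SAP abolishes the comparison altogether; SAP 14.6 shows that it does not. A reader might also infer that the model works on a scale foreign to the primary analysis; IR* shows otherwise. Nor does the sample-size basis call for a confirmatory test.

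It does not dispose of the point. Choosing a different model is within the delegation; barring the comparison in the primary analysis is not. The remaining coefficient is secondary and adjusted for covariates picked by P-value, so it is not the simple overall contrast of 7.6.2. A difference that a reader can work out is not one that the plan commits to report. None of these arguments makes the declaration of no changes accurate.

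**Conclusion.** The point holds as an undeclared mismatch between protocol and SAP and should be fixed. The contrast is demoted, not lost. What is missing is a pre-specified, unadjusted overall EMG-MG estimate in the primary analysis and a record that the protocol's plan was altered.

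The size is one of precision, not bias. The missing difference would have a 95% half-width of 4.6 to 5.3 points at rates of 25% to 45% with one outcome per woman. At 35% with one to three embryos, it would be about 3.0 to 5.9 points on nFS/nET and 3.0 to 5.1 on IR*. These figures assume that all 1500 women have a transfer. SAP 17 codes cancelled transfers and freeze-all as exits, so the real intervals would be somewhat wider. Embryo numbers and within-woman correlation are assumptions.

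A reader might infer from the P > 0.10 rule that treatment itself would often be eliminated. The documents do not establish that. SAP 14.6 names treatment as the independent parameter and lists the confounders separately, so the rule may well be meant for the confounders only. The defect is that treatment is not expressly exempt. The subgroup P-values are optional; they make the descriptive label inconsistent but are not planned as a substitute for the overall comparison.

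**What to change.** - In SAP 14.1 add one overall unadjusted EMG-MG rate ratio with 95% CI from the protocol's Poisson model: nFS as outcome, offset log(nET), robust standard errors clustered on woman. Label it exploratory and estimation-focused. Women without a transfer have no offset and drop out; report their number per arm.
- Optionally add the difference in IR* with 95% CI. The Poisson model with this offset gives a ratio, not a difference.
- State beside the estimate that it uses the grouping of SAP 8.1, which is by method used, unless that is changed.
- In SAP 14.6 state that treatment is retained whatever its P-value. Reconcile the descriptive label in 14.1 with the optional subgroup P-values.
- Replace the declaration of no changes with a record of, and reason for, any remaining departure from protocol 7.6.2.

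The cost is SAP wording and one added model, with no further data or patients.
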